Side Effects/Risks: The risks associated with SSM are considered low for subjects who meet the inclusion/exclusion criteria; to further minimize risks licensed doctors of chiropractic (DC) and physical therapists (PT) will be trained and certified by investigators, and monitored for fidelity to ensure they are implementing SSM in a manner that optimizes patient safety. Experienced investigators and consultants will be readily available as needed to consult with DCs and PTs to clinically manage adverse events as needed. The core elements of SSM include physical and psychosocial strategies.

Physical: Side effects associated with manual treatment and exercise are common and benign. Approximately 35% of participants in our previous BRLP trial reported expected self-limiting adverse events that were mild to moderate in severity (e.g. increased pain, soreness).²⁰ Serious adverse events following manual treatment to the lower back are rare and are estimated to occur once per million to several million visits and include cauda equina syndrome, disc herniation, fracture, hematoma or hemorrhagic cyst.^{31, 146}

[figure not shown]
Psychosocial. Subjects may experience some short-lasting emotional discomfort during and outside the sessions when practicing the psychosocial exercises and strategies

(e.g. of relaxed breathing, guided imagery, pacing, relaxation, pacing, problem solving, cognitive restructuring, interpersonal communication, etc.).

Providers: Licensed PTs and DCs with a minimum of 3 years of clinical experience will be provided an estimated 30 hours of training.

Training: The goal of SSM training is to facilitate providers' confidence and ability to act as an effective coach for patients' in their self-management. We will use methods effectively implemented in the investigators' previous and ongoing studies including video presentations, demonstrations, and simulated patient practice with feedback from investigators responsible for the SSM intervention ([name]).

Training content will include the essential information related to the core intervention elements and BCTs, and will emphasize patient-centered communication as a key part of delivery.¹⁵ Clinicians will be assessed for key competencies prior to certification. Competencies will be adapted from ongoing and previous studies with input from The Clinician Advisory Panel comprised of PTs and DCs during the **Aim 1** Planning Phase.

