6.2.4 Follow-up Visits

Intervention Visits (M0-M6)

The following information will be collected at each intervention visit in the pilot study, which will occur as needed throughout the six months, as there is no set schedule of treatments:

- Treatment administered – study providers will record treatment administered at each visit including required, allowed, and prohibited treatments.
- Adverse events (AEs)- participants will be asked about the occurrence of AE/SAEs by their treatment provider at each visit. The AE protocol described in section 7, Safety and Assessments will be initiated and adhered to for all AEs identified.

Weekly Follow-Up (\pm 3 DAYS)

Weekly outcomes will be collected electronically via direct patient self-report for six months; participants who are unable to provide electronic data will be contacted directly by blinded study staff who will ascertain outcomes. Additional information related to data collection and quality assurance is described in section 10.

Clinical Outcome Measures

- BRLP and LBP frequency and intensity

Monthly Follow-up (\pm 14 DAYS)

Monthly follow-up data (Months 1-6) will be collected electronically via direct patient self-report. Participants who are unable to provide electronic data will be contacted directly by blinded study staff who will ascertain outcomes, or they will be mailed a paper copy of the questionnaire to complete and return to the study team. Additional information related to data collection and quality assurance is described in section 10.

The following outcomes will be collected on a monthly basis for 6 months (\pm 14 days):

Clinical Outcome Measures

- Disability, PROMIS-29+2 measures, and productivity loss
- Adverse Events - participants will be asked if they experienced any potential adverse events associated with study interventions (e.g. increased pain, neurological symptoms, nausea)

Behavioral Outcome Measures

- BRLP-related medication and healthcare use

Month 2 Follow-up (\mp 14 DAYS)

Mediating Outcome Measures

- Satisfaction related to the patient-provider connection and healthcare environment (HEAL items).¹³⁵ Treatment expectations for the assigned intervention will also be assessed.

Month 3 Follow-up (\mp 14 DAYS)

Clinical Outcome Measures

- PROMIS/NIH Toolbox measures for social emotional support, domain-specific life satisfaction, and perceived stress.
- Global improvement will be measured using a 9-point scale ranging from completely recovered to vastly worse.¹⁵⁴

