7. SAFETY ASSESSMENTS

7.1. AEs and SAEs, Expectedness, and Relatedness- Definitions

The Co-PIs are responsible for adjudicating AEs/SAEs.

Adverse Event

AE is generally defined as any unfavorable and unintended diagnosis, symptom, sign (including an abnormal laboratory finding), syndrome or disease which either occurs during the study, having been absent at baseline, or if present at baseline, appears to worsen. AEs are to be recorded regardless of their relationship to the study intervention.

The following scale will be used to grade AEs:

1. Mild: no intervention required; no impact on activities of daily living (ADL).
2. Moderate: minimal, local, or non-invasive intervention indicated; moderate impact on ADL.
3. Severe: significant symptoms requiring invasive intervention; subject seeks medical attention, needs major assistance with ADL.

We will measure and compare rates of AEs across the two treatment arms. We will specifically look for common treatment-related AEs that include: LBP, soreness at the treatment site, gastrointestinal symptoms, emotional discomfort, and other events. We will capture AEs prospectively from study participants through monthly surveys and at intervention visits. Each unique occurrence will receive a separate ID in order to avoid duplication in documentation.

Serious Adverse Event

SAE is generally defined as any untoward medical occurrence that

- results in death
- is life threatening
- requires inpatient hospitalization or prolongation of existing hospitalization

- results in persistent or significant disability/incapacity, or is
- a congenital anomaly or birth defect.

We will collect SAEs both passively through ad hoc reporting and through systematic evaluation at study visits. Given the nature of the interventions we do not anticipate any specific treatment-related SAEs and therefore focus on standard and BRLP-specific serious events: death; severe or permanent disabilities; life-threatening conditions; hospitalizations; other important medical events; progressive neurological deficits, or cauda equina syndrome.

Expectedness:

AEs and SAEs will be classified as expected if

- They have been documented as a known adverse reaction (disclosed in the consent form) or are part of an existing comorbid disease process. The PI or designee is responsible for making this determination.

Relatedness to Research Participation:

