7.5. Known Expected Risks

Supported Biopsychosocial Self-Management

The risks associated with SSM are considered low for subjects who meet the inclusion/exclusion criteria. To further minimize risks, licensed doctors of chiropractic (DC) and physical therapists (PT) will be trained and certified by investigators, and monitored for fidelity to ensure they are implementing SSM in a manner that optimizes patient safety. Experienced investigators and consultants will be available as needed to assist DCs and PTs in managing adverse events if needed. The core elements of SSM include physical, psychological and social strategies.

Physical: Side effects associated with manual treatment and exercise are common and benign. Approximately 35% of participants in our previous BRLP trial reported expected self-limiting adverse events that were mild to moderate in severity (e.g. increased pain, soreness).²⁰

Serious adverse events following manual treatment to the lower back are rare and are estimated to occur once per million to several million visits.

Psychological and social: Subjects may experience some short-lasting emotional discomfort during and outside the sessions when practicing the psychological and social exercises and strategies (e.g. of relaxed breathing, guided imagery, pacing, relaxation, pacing, problem solving, cognitive restructuring, interpersonal communication, etc.).

Expected risks include

- Cauda equina syndrome
- Disc herniation
- Emotional discomfort
- Exacerbation of low back pain/back related leg pain, soreness or stiffness in the region treated
- Fracture
- Hematomas or hemorrhagic cysts.^{31, 146}

Medical Care

The risks associated vary depending on the medications prescribed. Choice of first and second-line medications for the study protocol was informed by the current evidence and the American College of Physicians guidelines on noninvasive treatment for LBP which balances evidence for risks and benefits when making recommendations. Licensed medical providers will care for participants randomized to medical care. Pharmacological therapies are associated with increased adverse events compared to placebo.³¹ Study providers will discuss risk/benefit profiles for specific medications with participants before making a shared decision on what medication to prescribe.

Expected risks include:

- Non-steroidal anti-inflammatory drugs (First-Line Medications)

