 - Serious risks include cardiovascular events (heart attack, stroke, heart failure, high blood pressure), gastrointestinal bleeding, allergic reaction (hives, skin irritation, respiratory distress, edema), kidney failure, skin reactions, liver failure, and asthma attacks.
 - Other side effects include stomach pain, constipation, diarrhea, gas, heartburn, nausea, vomiting and dizziness.
- Second-line medications
 - Serious risks with these medications include allergic reaction, seizures, infection, hyperglycemia, bone fracture, liver or kidney damage, and addiction or abuse.
 - Other risks include sedation, drowsiness, fatigue, sleep problems, headache, weight gain, muscle weakness, mental/physical impairment, dry mouth, abdominal pain, anorexia, nausea, vomiting, gastritis, occult bleeding, dizziness, vertigo, tremor, syncope, and leukopenia.

Pilot study and supplemental aims qualitative data collection: there are few risks associated with this data collection. Risks include feeling uncomfortable answering certain questions; to minimize this, participants can decline responding to questions

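### The AE types that Section 7.1 will look for match SSM's expected non-serious harms by category but cover only the gastrointestinal ones for Medical Care, which could tilt the between-arm AE comparison

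*Combined protocol and SAP*

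**What the plan says.** Section 7.1 commits to a comparison: "We will measure and compare rates of AEs across the two treatment arms". It then says what will be sought: "We will specifically look for common treatment-related AEs that include: LBP, soreness at the treatment site, gastrointestinal symptoms, emotional discomfort, and other events". The same section sets a wide recording rule: "AEs are to be recorded regardless of their relationship to the study intervention".

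Section 7.5 lists the expected risks of each intervention. For SSM the non-serious ones are "Exacerbation of low back pain/back related leg pain, soreness or stiffness in the region treated" and emotional discomfort ("Subjects may experience some short-lasting emotional discomfort during and outside the sessions"). The other SSM risks in that list are those that Section 5.1.1 classes as serious; they "include cauda equina syndrome, disc herniation, fracture, hematoma or hemorrhagic cyst".

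For Medical Care, Section 7.5 gives eight non-serious NSAID effects, seven of them gastrointestinal, and a longer second-line list that begins: "Other risks include sedation, drowsiness, fatigue, sleep problems, headache, weight gain, muscle weakness, mental/physical impairment, dry mouth".

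In the monthly survey (Section 6.2.4), "participants will be asked if they experienced any potential adverse events associated with study interventions (e.g. increased pain, neurological symptoms, nausea". Section 7.2 adds a general enquiry about AEs at every treatment visit and in every monthly questionnaire, and lets participants report to staff at any time.

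**The concern.** When two arms have different harm profiles, a comparison of AE rates is fair only if both profiles are elicited with the same completeness. Three of the four types named in Section 7.1 (LBP, treatment-site soreness, emotional discomfort) are SSM's expected harms, and the fourth is the gastrointestinal part of Medical Care's. Drowsiness, headache, vertigo, tremor, fainting and most other second-line drug effects fall into the open category at the end of the list.

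If events in that category are picked up less completely, drug harms are under-counted relative to SSM harms and SSM looks relatively worse. Section 6.2.4 may add to this, because it asks about events linked to the study interventions. A participant could leave out a symptom not attributed to treatment, although Section 7.1 wants AEs recorded whatever their cause.

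A larger sample does not remove an elicitation imbalance, so an AE form carried unchanged into the phase II trial would take the problem with it.

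**Working it through.** The plan gives no coverage figure, test or power for the AE comparison, so there is no figure of its own to reproduce. The check is a count of Section 7.5 terms against the four types named in Section 7.1, followed by an illustration of size.

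**SSM.** Both non-serious bullets in Section 7.5 match a named type (2 of 2). Term by term, 3 of 5 are named literally: low back pain, soreness and emotional discomfort. Leg pain and stiffness are covered only by a generous reading.

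**Medical Care.** Only gastrointestinal (GI) symptoms are named. Among second-line terms, the strict GI count takes abdominal pain, gastritis, nausea and vomiting. The broad count adds anorexia, dry mouth and occult bleeding.

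| Section 7.5 terms | Total | Named, strict | Named, broad |
|---|---|---|---|
| NSAIDs | 8 | 7 (88%) | 7 (88%) |
| Second-line | 20 | 4 (20%) | 7 (35%) |
| Both, duplicates kept | 28 | 11 (39%) | 14 (50%) |
| Nausea, vomiting, dizziness counted once | 25 | 9 (36%) | 12 (48%) |
| Stomach and abdominal pain also merged | 24 | 8 (33%) | 11 (46%) |

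The result depends somewhat on grouping. Pairing sedation with drowsiness and dizziness with vertigo, and dropping leukopenia (not a symptom), gives 24 − 3 = 21 terms, of which 8 to 11 are named (38% to 52%).

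**Monthly survey.** Its examples are increased pain, neurological symptoms and nausea. They include one of SSM's three categories (pain) and omit soreness and emotional discomfort. Suppose neurological symptoms are added to the Section 7.1 types:
- read as dizziness, vertigo, tremor and syncope, strict GI coverage becomes (8 + 4)/24 = 50% or (9 + 4)/25 = 52%;
- read to include headache, muscle weakness, sedation and drowsiness as well, coverage runs from (8 + 8)/24 = 67% to (12 + 8)/25 = 80%.

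**Size (illustration on assumed inputs).** Let p be the true AE rate in both arms, u the share of Medical Care AEs of unnamed type, and d the capture of unnamed relative to named events. With SSM fully captured, the spurious SSM excess is p × u × (1 − d). Take p = 0.35, the rate that Sections 5.1.1 and 7.5 report from the earlier BRLP trial. Take u from 1/8 = 0.125 (NSAID terms only) to 16/24 = 0.667 (all distinct terms, strict).
- d = 1: 0 points for any u.
- d = 0.8: 0.35 × 0.125 × 0.2 = 0.9 points, to 0.35 × 0.667 × 0.2 = 4.7 points.
- d = 0.5: 0.35 × 0.125 × 0.5 = 2.2 points, to 0.35 × 0.667 × 0.5 = 11.7 points.

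**Precision for scale.** Section 9.1 gives 40 to 50 participants. Assuming equal arms, the 95% half-width of a difference at 35% is 1.96 × √(2 × 0.35 × 0.65 / n) = 29.6 points at n = 20 and 26.4 points at n = 25.

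**The case against.** The strongest reply is that Section 7.1 is narrative, not the instrument. Its list is open, every AE is to be recorded, Section 7.2 has both arms asked about any AE, and the opening of Section 5 has side effects entered on standardized visit forms. The survey form itself is not in the documents. This stands: a reader might infer that drug harms will be under-counted, but the documents do not show it, and full capture gives no bias.

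A reader might also infer that the monthly survey repeats the tilt. It does not visibly do so. Its examples leave out two of SSM's three categories, include nausea, and may cover several drug effects. How many is uncertain, since elsewhere the protocol uses neurological mainly for deficits linked to leg pain (Sections 3.3, 4.2 and 6.2.1).

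A count of terms is also not a share of events. Section 7.5 gives no frequencies, NSAIDs come first and are nearly fully covered, and the gap lies in drugs used only when NSAIDs fail or are not tolerated. The 35% rate comes from manual treatment and exercise, not medication. OTC drugs are allowed in both arms and rescue medication in SSM, so drug effects are not confined to one arm. PROMIS-29+2 asks about fatigue and sleep monthly in both arms, though as outcomes and not as AEs. Finally, no AE comparison appears in Sections 9.4 or 9.5, so no feasibility target depends on it.

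These points limit the size and certainty of the concern. They leave in place that the one list of AEs to be specifically sought is uneven between the arms being compared.

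**Conclusion.** The point holds in a limited form. The Section 7.1 list matches SSM's non-serious risks by category and about a third to just under half of Medical Care's distinct non-serious terms. The upper end reaches 50% to 52% under the most generous groupings. The gap is mostly in second-line drugs.

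The direction is conditional: if unnamed events are elicited less completely, the Medical Care rate is too low and SSM looks relatively worse. The 0 to 11.7 point range rests on an equal true rate of 35%, on term counts standing in for event shares, and on capture of unnamed events between 50% and 100% of that for named ones. None of these is established by the documents. Even the top of the range is well inside the pilot's sampling error. To say that the planned comparison is biased against SSM, or that every SSM risk is named, would go beyond the text. This is a cheap improvement, worth making mainly because the pilot prepares the phase II methods.

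**What to change.** In Section 7.1 and the monthly survey (Section 6.2.4), replace the illustrative examples with one fixed symptom checklist, identical in both arms and asked regardless of assigned treatment or perceived cause. Draw it from the symptomatic non-serious risks in Section 7.5 for both interventions:
- increased back or leg pain; soreness or stiffness; emotional discomfort; gastrointestinal symptoms, including appetite loss;
- drowsiness or sedation; dizziness or vertigo; headache; sleep problems; fatigue; muscle weakness; weight gain; dry mouth; tremor or fainting; mental or physical impairment;
- free text for anything else.

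State that the between-arm AE comparison uses this checklist and that volunteered AEs are reported separately. State also that it covers symptomatic events only: Table 5 schedules no laboratory test, and no physical examination after the first baseline visit, so effects such as leukopenia would not be detected by it.

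The cost is about ten extra tick-box items a month (14 lines less the four types already named in Section 7.1), IRB approval of the revised survey, and more minor AEs to log.

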7.2 Adverse Event Identification

Adverse events will be identified in the following ways:

- Following enrollment, participants will be asked about the occurrence of AE/SAEs by their treatment provider at every visit.
- Participants will be informed to report AE/SAEs directly to study staff throughout the study period
- Participants will be asked if they experienced any AE/SAEs during their monthly self-report questionnaires.

7.3 Follow-up for Adverse Events

Events will be followed until resolution or stabilization, whichever occurs first; resolution and stabilization will be determined by the PI with input from the study clinician when appropriate.

AEs During the Intervention Phase

If an AE/SAE occurs during the intervention phase, the study clinician or designee will obtain information about the event, which will be used by the PI to assess the severity, expectedness and relatedness to the study. The study clinician will monitor the AE/SAE while the participant is under their care; this will include a medical evaluation and treatment, or modifications to treatment as necessary to protect the participant and minimize harm. If warranted, referral to an outside provider will be made. Participants who cannot continue with the study intervention due to safety concerns will be removed from the intervention and/or study when warranted. See Study Discontinuation.

The rescue medication protocol may apply. See Rescue Medication.

AEs During the Monthly Follow-Up (M1-M6)

If an AE/SAE occurs during the follow-up phase, study staff (clinician, coordinator, PI or designee) will contact the participant (or their emergency contact with the participant's permission), to obtain information about the event, including but not limited to what happened, when the event occurred, and treatment rendered. This information will be used by the PI to assess the severity, expectedness and relatedness to the study.

Events will be followed for outcome information until resolution or stabilization. Resolution and stabilization will be determined by a PI with input from the study clinician when appropriate.

The PI or designee will record all reportable events with start dates occurring any time after enrollment until 7 (for non-serious AEs) or 30 days (for SAEs) after the last day of study participation.

7.4 Reporting Procedures

AEs/SAEs/Unanticipated problems will be reported to NCCIH and the UMN IRB. "Awareness" or "Aware" is defined as the date on which the research team is able to discuss the event with the participant (or their designee) to gather additional information about the event for adjudication. See AEs and SAEs, Expectedness, and Relatedness-Definitions for information related to how decisions will be made regarding determining relatedness and severity.

NCCIH

Unexpected fatal or life-threatening AEs related to the intervention will be reported to the NCCIH Program Officer within 3 days of the investigator becoming aware of the event.

Other serious, unexpected AEs related to the intervention will be reported within 7 business days.

UPIRTSOs will be reported within 7 business days.

All other AEs documented during the course of the trial will be summarized and reported to NCCIH on an annual basis by way of inclusion in the annual report and in the annual AE summary which will be provided to NCCIH.

UMN IRB

The UMN IRB will be notified via a Report of New Information (RNI) of *any harm* (e.g. AE or SAE) experienced by a participant or other individual that, in the opinion of the PI or designee, is *unexpected and at least probably related* to the research procedures within 5 business days of the study team becoming aware of the event.

Unexpected death: Unexpected death of a locally enrolled participant whether considered related to the research or not will be reported to the UMN IRB via a RNI within 5 business days of the study team being made aware of the event. Death is considered unexpected if the risk of death is not listed in the consent form.

If new information becomes available to the research team that suggests a new or increased risk to study participants, a safety issue or a reduction in benefit, this information will be reported to the UMN IRB via a RNI within 5 business days of the study team being made aware of the new information.

Effective March 27, 2017, submitting logs of events at continuing review is not required.

See Protocol Deviations for reporting information related to deviations and participant harm.

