10.3.4. Metrics

For each follow-up survey, we aim to achieve an 85% or higher follow-up rate. We will utilize a combination of web-based survey, telephone and text-based outreach, and mailed surveys to achieve maximal survey response. Survey completion rates will be primarily based upon the completion of pain and functional outcome measures, but we will additionally tabulate follow-up by each instrument to monitor and evaluate survey burden. Data on other key feasibility measures and targets will also be reviewed weekly

by the PIs and monthly by the Study Steering Committee (e.g. recruitment rates, enrollment rates, intervention acceptability, credibility, and adherence, provider fidelity, adverse event reporting).

Loss to Follow-Up: Participants are considered loss to follow-up if any of the criteria below are met:

1. Participant dies
2. Participant formally withdraws from the study
3. Participant misses 3 consecutive monthly and 8 consecutive weekly surveys without responding to reminders by email (at least 3) or phone (at least 3).

Participant's meeting criteria 3 can have their loss to follow up status removed if they contact the study and request continuation of data collection activities.

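### Section 7.4 starts the 3-day NCCIH clock and the event-based 5-business-day IRB clocks at a conversation with the participant or an undefined designee, with no fallback start

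*Combined protocol and SAP*

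**What the plan says.** Section 7.4 gives its own definition of *aware*: it "is defined as the date on which the research team is able to discuss the event with the participant (or their designee". The stated purpose of that discussion is to collect further information for adjudication.

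The timed reports follow in the same section. Fatal or life-threatening events judged unexpected and related "will be reported to the NCCIH Program Officer within 3 days of the investigator becoming aware of the event". For NCCIH it adds: "Other serious, unexpected AEs related to the intervention will be reported within 7 business days" and "UPIRTSOs will be reported within 7 business days". The IRB is to be told of unexpected harm that is probably or definitely related "within 5 business days of the study team becoming aware of the event". An unexpected death of a local participant goes to the IRB on the same 5-business-day limit, regardless of relatedness, counted from the team being made aware. A further 5-business-day IRB report covers new information that points to a safety issue or a changed risk.

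On whom to contact, section 7.3, in its text on the monthly follow-up, names the participant "or their emergency contact with the" participant's permission.

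**The concern.** A reporting clock normally starts when the team first learns of an event. Here it starts when a particular conversation becomes possible, and that may be later. The protocol itself foresees situations in which the two dates separate:

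- Section 7.2 makes the monthly questionnaire a source of adverse events, so the team can hold a written report before speaking to anyone.
- Section 10.3.4 expects some participants not to answer repeated email or phone reminders.
- Section 8 says that people who withdraw and decline further questionnaires are not contacted again, while section 7.3 records serious events until 30 days after the last day of participation.
- A participant who has died, or is too ill to speak, cannot hold the discussion, so everything then depends on the designee.

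The stake is the timeliness of the most serious reports, which carry the shortest deadline, while others are still being enrolled and treated. No feasibility target, sample size or analysis is affected.

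**Working it through.** The plan gives no figure to reproduce, so the check sets each deadline beside its written start and then works through the effect of a lag.

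**Step 1. The six timed reports in section 7.4**

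| Report | Limit | Written start | Tied to the definition? |
|---|---|---|---|
| NCCIH: unexpected, related, fatal or life-threatening | 3 days | investigator becomes aware of the event | Yes |
| NCCIH: other serious, unexpected, related | 7 business days | none stated | Unclear |
| NCCIH: UPIRTSO | 7 business days | none stated | Unclear |
| IRB: unexpected harm, probably related or more | 5 business days | team becomes aware of the event | Yes |
| IRB: unexpected death, related or not | 5 business days | team is made aware of the event | Yes, if the defined sense applies |
| IRB: new risk or safety information | 5 business days | team is made aware of the information | No; it does not concern discussing a participant's event |

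Three of the six count from awareness of an event, two have no start, and one counts from awareness of information.

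**Step 2. Is there a fallback?** Sections 7.1 to 7.4, 8 and 10.3.4 to 10.3.6 were read for a substitute start, a cap on the wait, or a definition of the designee. None is there. The consent form was not available for this check. If it names a designee or records advance permission to call the emergency contact, that would shorten the lag for some participants but would not change the definition.

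**Step 3. Effect of a lag.** Let L be the days from first knowledge to the discussion. The documents give no value for L, so the values below are assumptions.

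Due date of the 3-day report, counted from first knowledge = L + 3.

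- L = 0: 0 + 3 = 3 days
- L = 7: 7 + 3 = 10 days
- L = 14: 14 + 3 = 17 days

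The 5-business-day event reports move in the same way. With a lag of B business days they fall due B + 5 business days after first knowledge, so 5, 10 or 15 for B = 0, 5 or 10. If no discussion ever becomes possible, L has no value and the literal clock has no start date.

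**Step 4. Does adjudication need the conversation?** For the 3-day report and the related-harm report, expectedness and relatedness must be judged, and a discussion helps. For the death report the protocol removes relatedness from the test and judges expectedness against the risks listed in the consent form. That report can be made without a conversation, yet on the defined meaning it waits for one.

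**The case against.** The strongest reply is that the gap is narrower than the definition suggests, and much of that reply stands.

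- **The designee.** A reachable designee starts the clock. If family members report a death and one of them is the designee, first notice and awareness coincide. The permission condition on the emergency contact appears only in the follow-up text of section 7.3; the intervention-phase text has no such limit. Events raised at a treatment visit are usually discussed the same day.
- **Other routes.** Table 8 sends unexpected, related serious events to the independent monitor(s), NIH/NCCIH and the IRB per occurrence. The new-information report could also catch such an event without a conversation. But Table 8 sets no deadline, and the new-information report goes only to the IRB and depends on a judgement that the risk picture has changed.
- **Ordinary meaning.** *Being made aware*, in the death clause, could simply mean being notified. That reading conflicts with the definition in the same section, so the two need reconciling.

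Three stronger readings are tempting, and the documents do not support them. A reader might infer that every external deadline is caught; Step 1 shows otherwise.

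A reader might infer that the team could hold news of a fatal event for as long as it liked and still comply. The two other routes remain duties whether or not a discussion takes place.

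A reader might also take a delay from the loss-to-follow-up rule in section 10.3.4, "Participant misses 3 consecutive monthly and 8 consecutive weekly surveys without responding to reminders", and get 3 × 30 = 90 days, about half of the 6-month enrolment period. That status neither starts nor stops a reporting clock, so it does not measure the delay. A hospitalization ticked on a survey, unless life-threatening, falls for NCCIH under the 7-business-day limit, which has no stated start. Nor does the half hold in general. If someone enrolled at month t reports at month t + 3, a three-month delay overlaps enrolment by max(0, 3 − t) months. Under uniform accrual over 6 months the mean is (3 × 3 / 2) / 6 = 0.75 months, or 0.75 / 6 = 12.5%.

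**Conclusion.** The definition of awareness is wrong as written. It clearly governs the 3-day NCCIH clock and the IRB clock for related harm, and it governs the unexpected-death clock if the defined sense carries over. Each of these deadlines moves back by the lag between first knowledge and discussion. The text sets no upper limit on that lag, and the clock may not start when neither participant nor designee can be reached or contacted. The two 7-business-day limits have a separate defect, since no start is stated.

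The size cannot be put in days from the documents; L + 3 is exact, but L is an assumption. The conclusion rests on reading the definition literally and on there being no fallback elsewhere in the protocol. It is a correction of moderate weight to safety-reporting wording in a pilot of 40-50 participants, with adverse-event enquiry at every visit, monthly steering review and semi-annual independent review. It is worth making because it touches the gravest events.

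**What to change.** In section 7.4, define awareness as the calendar date on which any member of the study team (treating provider, coordinator, survey staff or investigator) first receives information, from any source including a submitted survey, that a reportable event may have occurred. State that this date starts the 3-day, the 7-business-day and the event-based 5-business-day reports, and use the same term in the death clause. Require an initial report on the information then held, and a follow-up report once the event has been discussed with the participant or designee. Record the discussion date separately.

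The cost is a short rewording of section 7.4 and one date field on the adverse event form. Some initial reports will be incomplete, and some events will later be adjudicated as unrelated or expected, so follow-up reports will be needed. No treatment rule, sample size or feasibility target changes.
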